9.3.12 CTI Ablation Failure

The endpoint is CTI Ablation Failure. The proportion of CTI-ablated subjects with CTI Ablation Failure in each treatment group will be analyzed descriptively: the number with the endpoint, the number evaluated, the percentage and 95% Bayesian credible intervals (BCIs) for the proportion in each group as well as the difference between groups will be presented. The posterior probability that $P_T < P_C$ will be presented. The statistical methods will be a Bayesian comparison of proportions (with predictions) as described in Section 19. Exploratory frequentist analyses may also be conducted.

9.3.13 Thermal Group RF Ablation / Cryoablation Effectiveness Assessment

The two control group technologies (radiofrequency ablation and cryoablation) will be evaluated and compared using methods analogous to the primary effectiveness analysis, only comparing RF to Cryo groups rather than Treatment to Control. The endpoint is Treatment Success. The proportion of subjects with Treatment Success in each control subgroup (RF, Cryo) will be analyzed descriptively: the number with the endpoint, the total number of subjects evaluated, the percentage, and 95% Bayesian credible intervals (BCIs) for the proportion in each group as well as the difference between groups will be presented. The posterior probability that $P_{RF} > P_{Cryo}$ will be presented. Exploratory frequentist analyses may also be conducted.

9.3.14 AF Symptom Assessment

The occurrence and number of patient-reported AF Symptoms (such as dizziness, palpitations, rapid heartbeat, dyspnea, fatigue, and syncope) at baseline and 12 months will be reported. For each symptom, the frequency of the symptom at each time point, as well as the proportion of subjects who indicate the presence of the symptom at baseline but not at 12 months, will be summarized with counts, percentages, and 95% Bayesian credible intervals (BCIs) for the proportions within each treatment group as well as the difference in proportions between treatment groups. In addition, the count of reported episodes of each symptom type at each time point, as well as the change in reported counts from baseline to 12 months, will be summarized

with means, standards of deviation, and 95% Bayesian credible intervals (BCIs) for the average within each group as well as the difference between groups.

9.3.15 Learning Curve Effectiveness Assessment

This is an analysis of both a per-operator and a per-site learning curve in the Treatment group by enrollment sequence. Patient order will be determined by sequential procedure order by either the operator or the site, determining whether the procedure would be placed in the (1-3) group, (4-6) group, or the (>6) group.

The number of subjects with Acute Procedural Success by experience category, the total number evaluated, the percentage, and the results of the Fisher-Freeman-Halton test for each operator and site will be presented. The analysis will also be conducted using Treatment Success as the endpoint. Supportive analyses of procedural metrics may be performed.

10 Safety Analyses

Unless specifically identified below, all safety analyses will be performed in the Safety Population as the principal analyses. Supportive analyses will be conducted in the Per Protocol (PP) population.

10.1 Primary Safety Analysis

The primary safety endpoint for this study is the Composite Safety Endpoint (CSE) defined in Protocol Section 7.1.

The analysis of the primary safety endpoint is a test of non-inferiority of the event rate at 12 months. The null and alternative hypotheses are:

$$H_0: Q_T \geq Q_C + 0.08 \text{ versus } H_A: Q_T < Q_C + 0.08$$

where Q_T is the CSE proportion in the Treatment Group, and Q_C is the CSE proportion in the Control Group. The differences in the proportion of subjects with one or more CSE events between the Treatment Group and the Control Group will be tested with a Bayesian statistical method that is analogous to that used in the primary effectiveness analysis. The prior distributions for Q_T and Q_C in these calculations are Beta (0.5, 0.5), which is the Jeffreys non-informative prior. Q_T will be determined to be non-inferior to Q_C if it can be established that the posterior probability $Pr(H_A | \text{data}) > \Psi_{\text{saf}}$, where $\Psi_{\text{saf}} = 0.966$ is a pre-specified threshold value that controls the one-sided type I error rate (under simulation) at level 0.05. In the absence of missing data, the posterior distributions for Q_T and Q_C would be conjugate Beta distributions. However, some missing data are expected. Therefore, Bayesian multiple imputation of 12-month outcomes will be employed in the principal analysis. The imputation model accounts for primary outcome information up through the time of censoring. More detail on this imputation is given in Section 13.2.

10.2 Secondary Safety Endpoint Analyses

10.2.1 PV Dimensional Change: Aggregate PV Cross-Sectional Area

The first secondary safety analysis is an analysis of Aggregate PV Cross-Sectional Area. Aggregate PV Cross-Sectional Area approximates the ability of blood to return to the left atrium.

The cross-sectional area of an individual vein is computed using the formula for area of an ellipse, where the longest and shortest axis measurements of the PV diameter serve as the major and minor axes of the ellipse. “Aggregate PV Cross-Sectional Area” is the within-subject sum of the cross-sectional areas of the following veins:

- Left Superior Pulmonary Vein (LSPV)
- Left Inferior Pulmonary Vein (LIPV)
- Right Superior Pulmonary Vein (RSPV)
- Right Inferior Pulmonary Vein (RIPV)

For subjects with a Left Common Pulmonary Vein (LCPV), the Net PV Cross-sectional Area will be computed using the LCPV area in lieu of the LSPV and LIPV areas. The areas of any Right Middle PVs will be ignored, since they are small, rare, and often not ablated.

This analysis will be conducted on a per-subject basis, using paired (pre- and post-ablation) continuous measurements of Aggregate PV Cross-Sectional area at baseline and 3 months. Within-subject changes in Aggregate PV Cross-Sectional Area (3-month minus baseline) will be compared between Pulsed Field and Thermal groups via a Bayesian version of a t-test, as described in Section 19.1. The null and alternative hypotheses are:

$$H_0: \mu_T - \mu_C = 0 \text{ versus } H_A: \mu_T - \mu_C > 0,$$

where μ_T represents the change (3 months minus baseline) in area in the treatment (Pulsed Field) group, and μ_C represents the corresponding change in area in the control (Thermal) group. (If the pulmonary veins tend to narrow more in the Control group than in the Treatment group, the post-minus-pre differences will be “more negative” in the Control group than in the Treatment group, resulting in $\mu_T - \mu_C > 0$.) The null hypothesis will be rejected if the posterior probability $P(H_A | \text{data})$ exceeds a threshold value $\Psi_{PV} = 0.975$, corresponding to a one-sided significance level of 0.025.

Exploratory comparisons (e.g., areas and diameters for each vein and for radio frequency vs cryoablation treatment technologies) will also be conducted, and these may use Bayesian or frequentist statistical methods, but these will be outside of the formal familywise error rate control described in Section 6. When diameters are computed, they will be the geometric mean of the longest and shortest axis measurement.

The population for analysis will be MITT Subjects with pre- and post-procedure PV dimensional data related to one or more protocol-specified ablation lesions. Supplemental analyses will be performed using MITT single-procedure subjects and the PP population.

Type I Error Considerations

This analysis is only conducted once (at the final analysis). Therefore, Type I errors can only arise from the test of the model above, without inflation from the sampling plan.

Since the prior distributions for all parameters are uniform, essentially all information in the model is contained within the likelihood. Therefore, a rule that determines $P(H_A | \text{data}) > \Psi$ must induce a “critical value” in the data space that is approximately equal to the critical value defined by a $(1 - \Psi)$ -level significance test in the setting of a standard frequentist hypothesis test, and the type 1 error rate must therefore closely approximate the quantity $1 - \Psi$. This is consistent with the statement of Gelman et al. that “in various simple one-sided hypothesis tests, conventional p-values may correspond with posterior probabilities, under noninformative prior distributions”¹² and the

statement of Albert that "a Bayesian probability of a hypothesis is equal to the p-value for one-sided testing problems when a vague prior distribution is placed on the parameter."¹³ It follows that using a posterior probability threshold $\Psi_{PV} = 0.975$ for this test will control the type I error rate at the level 0.025.

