## 7.2 Secondary Safety Endpoint

The secondary safety endpoint is Aggregate PV Cross-Sectional Area, defined as the paired comparison of change in the computed Aggregate PV Cross-Sectional Area (**Section 6.3.14**) between baseline and 3 months in MITT subjects compared between randomization groups (intent-to-treat, regardless of re-ablation with any second energy modality). Supplemental analyses will include MITT single-procedure subjects and the PP population.

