## 9.9 Assessment of the Secondary Safety Endpoint

One endpoint – Aggregate PV Cross-Sectional Area (Section 7.2) – will be formally tested as a secondary safety endpoint.

The paired comparison of change in the Aggregate PV Cross-Sectional Area between baseline and 3 months will be compared between Pulsed Field Subjects and Thermal Subjects, testing whether the reduction in Aggregate PV Cross-Sectional Area is significantly less in the Pulsed Field Subjects. Within-subject changes in Aggregate PV Cross-sectional Area (3-month minus baseline) will be compared between Pulsed Field and Thermal groups via a Bayesian version of a t-test. The null and alternative hypotheses are:

$$H_0: \mu_T - \mu_C = 0 \text{ versus } H_A: \mu_T - \mu_C > 0,$$

where  $\mu_T$  represents the change (3 months minus baseline) in area in the treatment (Pulsed Field) group, and  $\mu_C$  represents the corresponding change in area in the control (Thermal) group. The null hypothesis will be rejected if the posterior probability  $P(H_A | \text{data})$  exceeds a threshold value  $\Psi_{PV} = 0.975$ , corresponding to a one-sided significance level of 0.025.

The population for analysis will be MITT Subjects with pre- and post-procedure PV dimensional data related to one or more protocol-specified ablation lesions.

Supplemental analyses will be performed using MITT single procedure subjects and the PP population.

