5.6 Additional Safety Endpoints

1. Severe Ablation Complications (Protocol Section 7.3.1): The proportion of subjects in each treatment group with one or more of the following CSE components (as defined in Protocol Section 7.1, Table 4) will be compared between treatment groups.
 - a. PV stenosis
 - b. Persistent phrenic nerve palsy
 - c. Atrio-esophageal fistula
2. Nonserious / Serious CSEs (Protocol Section 7.3)
3. Post-Blanking Cardioversions (Protocol Section 7.3)
4. Post-Blanking Arrhythmia Hospitalizations (Protocol Section 7.3)
5. Any Related SAE (Protocol Section 7.3)
6. Any Related Stroke or TIA (Protocol Section 7.3)
7. Categorized PV Dimensional Changes (Protocol Section 7.3)
8. Control RF Ablation / Cryoablation Safety Assessment (Protocol Section 7.3)
9. Learning Curve Safety Assessment (Protocol Section 7.3)

6 Multiplicity

The study will be considered successful only if non-inferiority is established at the final analysis for the primary effectiveness endpoint and for the primary safety endpoint. Two secondary superiority tests are also formally pre-specified: (1) Aggregate PV Cross-Sectional Area, and (2) superiority using the primary effectiveness metric of Treatment Success. These will be tested in the above order, each at the 0.025 significance level (one-sided); the hypothesis for superiority of Treatment Success will not be formally tested unless the endpoint of Aggregate PV Cross-Sectional Area has demonstrated statistical significance. Neither secondary test will be conducted if the primary non-inferiority tests for effectiveness and safety do not establish non-inferiority.

7 Comparability Analyses of the Patient Populations

These analyses are intended to determine the similarity of treatment groups and study sites with respect to important demographic or other variables, either known or suspected to have an influence on the outcome variables. The absence of similarity for any baseline variable will identify that variable as a potential covariate in subsequent safety and effectiveness sensitivity analyses. The data for each baseline variable will be presented descriptively. For quantitative variables like age, the mean, standard deviation (SD), median, minimum, and maximum will be presented. For qualitative variables like gender, the number with the characteristic, the total number evaluated, and the percentage will be presented.

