7.1 Comparability between Treatments

The comparison of baseline characteristics across treatment groups will apply the following methods. Continuous variables such as age will be compared with two-sided $\alpha=0.05$ Wilcoxon rank sum test or two-sample t-test, and qualitative variables will be analyzed with χ^2 tests, Fisher's exact test or Fisher-Freeman-Halton test. Any important variable found to significantly differ across treatment groups will be considered as a possible covariate in subsequent multivariate safety or effectiveness analyses.

Comparability will be assessed with frequentist statistical tests, but the primary analysis of study results uses Bayesian statistical methods. Tables of baseline demographics or clinical variables in the clinical study report will be summarized using descriptive statistics. Where appropriate, inferential summaries that are consistent with Bayesian methods (such as 95% Bayesian credible intervals) will be presented. The methods used for these summaries are presented in Section 19.

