16.3 Other Sensitivity Analyses

- A sensitivity analysis of the Primary Effectiveness Endpoint will also be conducted, in which subjects requiring ablation for an accessory pathway, AVNRT, treatment-emergent left AFL, or incessant AT are counted as treatment failures.
- As indicated in Section 9, the primary analysis for effectiveness will be conducted in the mITT population, but supportive analyses will also be conducted in the PP population. Similarly, as indicated in Section 10, the primary analysis for safety will be conducted in the Safety Population, supportive analyses will also be conducted in the PP population.
- For the primary effectiveness endpoint, Kaplan-Meier estimates of event rates will also be presented.

17 Heterogeneity/Poolability

Incidence of the primary safety and primary effectiveness endpoints will be evaluated for poolability across key subgroups. In particular, the primary endpoints will be examined for differences between sexes and sites. A specific categorization of sites is those that use RF as the control therapy and those that use cryoablation as the control therapy. Poolability of treatment effect over this factor (site uses RF, site uses cryo) will also be studied.

Poolability tests will be conducted with frequentist methods. For each factor of interest (sex, site), a logistic regression will be fit, with predictors Treatment Group, the factor, and their interaction. If the interaction p-value is significant at the level 0.15, further analyses will be conducted. At a minimum, any baseline variables found to differ between treatment groups and any baseline variables found to significantly predict a primary event (Treatment Response, or occurrence of CSE) in univariate analyses will be candidates for inclusion in logistic regression adjustment to see whether the apparent heterogeneity is explained by these factors. If so, analyses that adjust for these factors will be presented. If not, further analyses will be conducted, including presenting results separately by sex / site.

Sites with fewer than 8 subjects will be considered small sites. Poolability analyses will be summarized descriptively for all sites, but inferential tests of poolability across sites will exclude small sites. If there are many small sites, or many sites with 0 events, inferential tests of poolability across sites may not be conducted.

18 Other Planned Analyses

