Normal Approximation

For large sample sizes, the t -distribution is well approximated by a Normal distribution, and the difference of two t -distributions is thus the difference of 2 Normal distributions, which is Normally distributed.

More specifically, approximating a t_{n-1} distribution by a Normal distribution with the same mean and variance,

$$\left[\frac{\mu - \bar{x}}{s/\sqrt{n}} \right] \sim t_{n-1} \approx N \left(0, \frac{n-1}{n-3} \right),$$

and thus $(\mu_T - \mu_C)$ is approximated by a Normal distribution with mean $(\bar{x}_T - \bar{x}_C)$ and variance $\left(\frac{(n_T-1)s_T^2}{n_T(n_T-3)} + \frac{(n_C-1)s_C^2}{n_C(n_C-3)} \right)$. Posterior probabilities and quantiles for $(\mu_T - \mu_C)$ can then be computed from this Normal distribution.

Unless otherwise specified, all implementations of this Bayesian t-test will use the (exact) Numerical Integration approach, above. Specifically, the test of PV Dimensional Change: Aggregate PV Cross-Sectional Area (Section 10.2.1) will use the Numerical Integration approach.

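### The formal test of Aggregate PV Cross-Sectional Area is valid but unadjusted; pre-specifying baseline area as a covariate would largely remove the effect of chance baseline imbalance at little cost

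*SAP*

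**What the plan says.** Protocol 7.2 defines the endpoint as "the paired comparison of change in the computed Aggregate PV Cross-Sectional Area" between baseline and 3 months. SAP 10.2.1 and Protocol 9.9 analyse it with the same two-sample test. In the SAP, within-subject changes in area ("3-month minus baseline) will be compared between Pulsed Field and Thermal groups via a Bayesian version of a t-test"; in the protocol, the changes "will be compared between Pulsed Field and Thermal groups via a Bayesian version of a t-test". The test succeeds if the posterior probability exceeds 0.975.

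The model in SAP 19.1 has a mean and a variance for each arm and no regression term. Its computation is fixed: "Specifically, the test of PV Dimensional Change: Aggregate PV Cross-Sectional Area (Section 10.2.1) will use the Numerical Integration approach".

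The analysis set is also fixed: "The population for analysis will be MITT Subjects with pre- and post-procedure PV dimensional data related to one or more protocol-specified ablation lesions". The supplemental analyses (single-procedure MITT and per protocol) change the population and not the model.

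Covariates appear only in later, data-driven work. Under SAP 7.1, an important variable found to differ between arms "will be considered as a possible covariate in subsequent multivariate safety or effectiveness analyses". SAP 7.2 allows site, or a variable that differs across sites, in sensitivity analyses. SAP 17 adds, for poolability of the primary endpoints, "any baseline variables found to significantly predict a primary event (Treatment Response, or occurrence of CSE"). None of these pre-specifies baseline area for this test.

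The test is a gate (SAP 6): "the hypothesis for superiority of Treatment Success will not be formally tested unless the endpoint of Aggregate PV Cross-Sectional Area has demonstrated statistical significance".

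**The concern.** A change score fixes the slope of 3-month area on baseline area at 1. If the true slope is different, subjects with larger veins at baseline change by a different absolute amount, and a chance baseline difference between arms enters the estimated treatment difference. Averaged over randomisations the effect is zero. In the one trial that is run, it is not.

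A subject contributes a change only if a baseline area exists, so the covariate is complete. The plan looks at baseline differences only after the data are seen. An adjusted result prompted by an observed imbalance would therefore be post hoc and outside the formal test. Because this test gates the superiority claim, its estimate should be as little exposed to chance as is cheaply possible.

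**Working it through.** **Plan's own figure.** 1 - 0.975 = 0.025. Simulating the Section 19.1 test (200,000 trials per case) gives type I error of 0.0246 (equal SDs) and 0.0241 (SDs 9.9 and 16.3) at 175 per arm, and 0.0256 and 0.0248 at 375 per arm. The stated level reproduces.

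**Inputs.**
- Allocation is 1:1, stratified by site, in permuted blocks (Protocol 9.2). The smallest sample is 350, or 175 per arm.
- Table 1 (Protocol 1.4.4) gives mean diameter changes of -11.8% and -12.7% for RFA, and +1.7% and +3.4% for PFA.
- The documents give no SD, correlation, expected difference or power for aggregate area.
- Assumed: area change is proportional to baseline area. The grid has 36 points: baseline CV c of 0.20, 0.25 or 0.30; per-subject SD s of proportional change of 0.05, 0.10 or 0.16 (Pulsed Field) and 0.10, 0.15, 0.20 or 0.27 (Thermal).

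**Slopes of change on baseline.**
- RFA: 0.882 x 0.873 - 1 = -0.230
- PFA: 1.017 x 1.034 - 1 = +0.052
- Average: -0.089

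**Effect of imbalance, equal arms.** The planned estimate carries the average slope, -0.089, times the baseline difference. An unweighted pooled slope estimates the same -0.089, so the carry-over is about 0. At 175 per arm, a 1.96-SE imbalance is 1.96 x sqrt(2/175) = 0.21 baseline SD.

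**Worked grid point** (c = 0.30, s = 0.05 and 0.10). With adjustment slope b (b = 0 for the planned test), the variance in an arm with mean proportional change m is (1 + c²)s² + (m - b)²c².
- Planned: 0.00296 + 0.01566 = 0.01863
- Adjusted, b = -0.089: 0.00451 + 0.01268 = 0.01719
- Ratio: 0.923
- Shift at a 1.96-SE imbalance: 0.089 x 0.21 x 0.30 = 0.0056. The planned SE is sqrt(0.01863/175) = 0.0103, so the shift is 0.54 SE.

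**All 36 points.**
- The variance ratio is 0.923 to 0.994, median 0.98. The interval is 0.3% to 3.9% narrower.
- The shift is 0.15 to 0.54 SE of the planned estimate.
- The Table 1 difference (0.282) is 11 to 30 SEs, and the shift is 1.3% to 2.0% of it.

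**Unequal arms.** With nT and nC in the Pulsed Field and Thermal arms and N in total, the planned test carries (nC·bT + nT·bC)/N and the pooled slope estimates (nT·bT + nC·bC)/N. The residual is (bT - bC)(nC - nT)/N.

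| Pulsed Field / Thermal | Planned | Residual | Share left |
|---|---|---|---|
| 175/175 | -0.089 | 0 | 0 |
| 160/190 | -0.077 | +0.024 (overcorrected) | 31% |
| 190/160 | -0.101 | -0.024 | 24% |

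The residual is 0.282 x 30/350 = 0.024. The variance ratio over both unequal splits is 0.91 to 0.996.

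**Other assumptions.**
- Equal SDs at both times: the ratio is (1 + r)/2, giving 0.85, 0.90 and 0.95 at r = 0.7, 0.8 and 0.9.
- A 3-month SD of 1.2 times baseline with r = 0.8: 1.44 x 0.36/(1 + 1.44 - 1.92) = 0.997.
- A quarter of the Table 1 effect: about 1.00.

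**Type I error given the imbalance** (normal approximation). The planned test has 0.039 and 0.015 at imbalances of -2 and +2 SE if the correlation of the estimate with the imbalance is -0.10, and 0.056 and 0.008 if it is -0.20. The grid implies correlations of about -0.08 to -0.28, since the squared correlation is 1 minus the variance ratio.

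**Does adjustment keep the level?** In five simulated null scenarios (175 per arm, 40,000 trials each), the pooled-slope test gave 0.022 to 0.026 and the planned test 0.021 to 0.024.

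**The case against.** The strongest case is that nothing is broken. The endpoint is defined as a comparison of change, and a two-sample test of change is its direct analysis. It is unbiased over randomisations and holds 0.025. The shift of up to 0.54 SE needs a 1.96-SE imbalance, which about 5% of trials exceed, and it is at most 2% of the Table 1 difference. All of this stands, and it limits how much weight the point can bear.

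The sizes also rest on assumptions. Table 1 is per vein, on diameters, and RFA only, while the plan keeps at least 40% of Thermal Subjects in either modality. At 19 of the 36 grid points the variance gain is under 2%. At the weakest point, simulation that includes estimation of the slope shows a ratio of 1.00. This stands too.

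It can further be said that adjustment adds risk to a gatekeeping test: the slope is estimated, both adjusted means share it, and Section 19.1 treats the two posteriors as independent. That is a reason to specify the method exactly. It is not a reason to refuse it, because the simulated type I error stays near 0.025.

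SAP 7 and the exploratory comparisons in SAP 10.2.1 would let an imbalance be examined, but only after it is seen and outside the formal test.

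Three stronger readings are tempting and unsupported. A reader might infer that the planned test inflates type I error; it does so only conditionally on an imbalance in one direction, with the opposite effect in the other. A reader might infer that adjustment abolishes the imbalance effect; it does so only for the linear part and only with near-equal arms. A reader might infer that the superiority test is at risk from an underpowered gate. Power is near 1.00 if Table 1 effects recur, and at a quarter of that effect it is 0.82 for both tests at the weakest grid point.

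**Conclusion.** The point holds as a low-cost improvement. The formal test is unadjusted, its covariate is already collected, and no pre-specified analysis uses it. Under proportional change at Table 1 rates, about 0.09 of any baseline difference passes into the estimate. An unweighted pooled slope largely removes this when the arms are near equal, as blocked 1:1 allocation should give.

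The precision gain is secondary: about 0.6% to 8% of the variance on the assumed grid, possibly nil, and larger only if baseline and 3-month areas correlate more weakly than that grid implies. The gate decision is unlikely to change if Table 1 effects recur. Confidence in these sizes is moderate, because the documents give no variance or correlation for aggregate area and no cryoballoon data on it.

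**What to change.** Before unblinding, amend SAP 10.2.1 and 19.1 and Protocol 9.9 to pre-specify:

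1. One pooled within-arm least-squares slope b of change on baseline aggregate area, not weighted by residual variance.
2. Adjusted change = change - b x (baseline - overall baseline mean).
3. The existing Section 19.1 t-test by Numerical Integration on the adjusted changes, with arm-specific variances and the same 0.975 threshold.
4. The unadjusted change test as a supplementary analysis.

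Two nearby versions should be avoided. A common slope fitted jointly with arm-specific residual variances is inverse-variance weighted. On the grid its variance ratio to the planned test is 0.947 to 1.032, so it can be about 3% less precise, and it leaves part of the imbalance effect. Arm-specific slopes need the variance of the estimated overall baseline mean; without that term, simulated type I error reached 0.039.

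The cost is one estimated slope, a restated type I error argument in SAP 10.2.1 (ideally with simulation, including unequal arms), and a short amendment submitted to the IRB and FDA under Protocol 13.4. No new data are needed. It could go in with another amendment.
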